The study will use cross-over, randomized, sham controlled, double-blinded design in which 15 participants with subacute or chronic ABI will be assigned to receive either active anodal spinal stimulation, cathodal spinal stimulation, and sham spinal stimulation experiments for the same duration in a random order. In all the experiments participants will receive exoskeleton-assisted training for duration of 1.5 hours. The first 20 minutes of training will be coupled with spinal

stimulation. Treatment will be administered at an intensity of 5 sessions per week for 2 weeks (Please see study HSC-MS-15-0269 PI: [name]).

Pre-screening Procedures: During the pre-screening process, potential subjects with ABI will be contacted by phone from research personnel. The aim and details of the study will be explained in details (reading from a phone script) and information such as demographics, medical history, medications being used, etc. will be gathered. Also ABI subjects will be screened for tsDCS and transcranial magnetic stimulation (TMS) contraindications (attachment 1, attachment 2) and a subgroup of patients (n=5) will be screened for MRI contraindications (attachment 3). The pre-screening will last about 30 minutes and will be performed in a private area. Once this information is collected, the coordinator will consult with the Drs. [name] (PI) and [name] and they will give final approval for the subject to come to The Institute for Rehabilitation and Research Memorial Hermann for the screening procedure.

Screening (Visit 1, duration: One hour): After subject arrives at TIRR a research personnel will meet him/her at the Motor Recovery Laboratory. The details of the study-specific procedures will be reviewed with the subject together. Subject will be screened for inclusion and exclusion criteria. Signed and dated informed consent will be obtained. Demographics, medical history, list of medications will be recorded. If the subject is female in child bearing ages, a urine pregnancy test will be requested. A medication diary will be given to the subject and asked to document all changes in type and dosage of the medication he/she has been using throughout the study. This will allow us to differentiate a potential effect of a change in dosage or type of medication on movement recovery. After subject meets all Inclusion and Exclusion Criteria he/she will be randomly assigned to active, cathodal or sham tsDCS group.

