Exoskeleton-assisted training: The side being trained (right vs left arm) will be weaker side of the body. Treatment will be provided by [name], in a dedicated therapy area in the UTHealth Motor Recovery Lab at TIRR-Memorial Hermann. Subjects will individually perform upper-extremity therapy exercises that are supported by the exoskeleton device. Activities that the subjects will be asked to perform will be selected based on the subject's upper-extremity motor function, including elbow flexion-extension, forearm pronation-supination, wrist flexion-extension, and radial-ulnar deviation. The tasks will be repeated multiple times per session for improved performance. Graphic feedback about performance will be given after each attempt in order to maintain motivation. Rest breaks will be given in order to avoid fatigue.

fNIRS: to measure brain activity over the treatment duration at the beginning of each session fNIRS system will be placed over the head of the subject. Brain activity will be recorded during rest (no active movement with the hand) and during movement (performing a motor task with hand).

Safety Assessment:

Questionnaire: At the end of each therapy session, tsDCS side effects questionnaire will be used to monitor any adverse events and study adherence (attachment 3). At the end of each session, the subject will describe any sensations they felt during stimulation and if they feel anything unexpected happened during the study visit. In addition the subject will be asked to rate his/her level of fatigue, pain, and satisfaction with the activities during the session.

Tolerability Assessment: Participants will be asked to rate the cervical spine unpleasantness and discomfort with a subject scale defining the level from “no discomfort at all” to “unbearable discomfort”.

Post-treatment and Follow-Up Assessment (Visit 13-15, duration: one and a half hours): During this period subjects will be asked to come within a-week after they have completed the study, at week-1 and month-1. Month-1 assessment will serve as the baseline assessment of the next treatment arm. Motor functions tests, exoskeleton measures and neurophysiological measurements with SSEP, TMS and fNIRS will be repeated after the treatment, at 1-week and at 3- months follow-up visits. MRI scan will be performed before and after treatment only.

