Portion of assessment sessions will be videotaped and/or photographed. Subjects will be asked to move or manipulate some objects with the arm while a project staff member will record or photograph. Subjects’ consent will be required to perform and photography or videotaping.

Screening, assessment and treatment sessions will be held at the UTHealth Motor Recovery Laboratory at The Institute for Rehabilitation and Research and at UTHealth Medical School, MRI Facility. A total of up to 42 visits are required. Each visit will take about one-and-a-half hour. Schedule of assessments is shown in Table 1.

Table 1. Schedule of assessments for adults with ABI for the first arm of the design. The subjects will undergo same study schedule in second and third treatment arms (See figure 1).

Assessment	Screening	Baseline Assessment	Intervention period											Post-treatment Assessment	Follow-Up Assessment at 1- week	Follow-Up Assessment at 1- Months		
	Day7- to Day1	Day 1	Day 4(±3) to Day 15(±3)											Day 19(±3)	Day 26 (±4)	Day 45 (±5)		
	Visit 1	Visit 2	Visit 3-12											Visit 13	Visit 14	Visit 15		
ICF	X																	
I/E Criteria	X	X																
Randomization	X																	
Demographics	X	X																
Medical History	X	X																
ASIA (motor and sensory score)		X														X	X	X
Modified Ashworth Scale		X														X	X	X
NHPT		X	X	X	X	X	X	X	X	X	X	X	X	X	X	X	X	X
Motor Activity Log		X	X	X	X	X	X	X	X	X	X	X	X	X	X	X	X	X
Grip Strength		X														X	X	X
Pinch Strength		X														X	X	X
JTHFT		X														X	X	X
FMA		X														X	X	X
Exoskeleton Measurement		X														X	X	X
tsDCS			X	X	X	X	X	X	X	X	X	X	X	X	X			
tsDCS related side effects			X	X	X	X	X	X	X	X	X	X	X	X	X			
MRI Scan		X														X		
TMS		X														X	X	X
SSEP		X														X	X	X
EEG		X														X	X	X
Spinal reflex		X														X	X	X
fNRIS		X	X	X	X	X	X	X	X	X	X	X	X	X	X	X	X	X
Adverse Events		X														X	X	X

[figure not shown]

Figure 1. The cross-over design of the study is illustrated. Abbreviations: Post-tx=Post-treatment assessment, EAAT= Exoskeleton -assisted arm training, tsDCS=transcutaneous spinal direct current stimulation, 1 w f/u= 1 week follow-up after the study intervention, 1 m f/u=1 month follow-up assessment after the study intervention.

Specimens to be collected, including frequency and size/amount: None.

5. SUBJECT POPULATION:

Fifteen adults with acquired brain injury (ABI) will be recruited from TIRR Memorial Hermann,

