2- After subjects are identified by their treating physicians and therapists, they will be referred to the co-investigator. During this first contact, the researcher will briefly explain the study content and request their phone number and e-mail address to contact them later for a pre-screening. During a phone call, a brief pre-screening procedure will be applied. Demographics and medical information such as surgery implants, medications, psychiatric, drug and alcohol history as inclusion and exclusion criteria will be gathered. Drs. [name] and [name] will review the information gathered during phone screening and may request more information about the surgery such as type of surgical implants, previous MRI notes, etc. In our experience with previous projects, we always needed to collect information from patients' medical record before the person could be enrolled into the study. For example if a surgery had been performed an approval from surgeon's office was requested to confirm the compatibility of surgical instruments with 3Tesla MRI. In some circumstances we further confirmed the surgical implants' compatibility with the manufacturing company. After all information are gathered Drs. [name] and [name] will agree or decline subject's enrollment into the study. A copy of consent form will be e-mailed to subject.

3- Potential subjects will be invited to come for a screening visit to Motor Recovery Laboratory at TIRR Memorial Hermann. Any information gathered during phone screening will be stored in a locked file cabinet and password protected electronic file. During the screening visit, an investigator at TIRR will obtain informed consent. The test procedures will be described and the testing equipment will be shown to the subject. A co-investigator will clearly explain all the procedures and risks of the testing outlined in the consent form. The subject will be given sufficient time to consider their decision and will be encouraged to ask questions, both during the initial interview and throughout the study. The PI or a co-investigator will answer any questions regarding the study at the time consent is given. Once enrolled, the subject may pause or terminate his/her participation at any time during the study.

4- Alternatively any person with ABI who are living in the community and been informed through flyers can contact the researchers directly and request more information about the study.

7. DATA ANALYSIS:

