Data analysis: Analyses will be performed with two-tailed significance tests at the 95% confidence level and are planned using parametric methods with continuous variables.

However, before performing parametric analyses we will examine the data for evidence of assumption violations and, if such violations are serious, we will perform data transformations or use non-parametric methods as appropriate. Four comparisons will be made. The primary efficacy variable will be the change in hand functions as measured with Jebsen-Taylor Hand Function test. Secondary outcome measures include change in strength of selective muscle groups, change in movement function and number of subjects who will reach minimally clinical significant change (ARAT), and muscle tonus (Modified Ashworth Scale) and change in movement smoothness (exoskeleton measurements), and change in the neurophysiological responses of central nervous system (TMS, SSEP). Adverse effects will be monitored with a Side Effects Questionnaire.

Within subject comparison of after treatment vs. baseline will be performed, separately for each group, using paired t-test. Second, a between groups will examine the effects of treatment by using a repeated measures of ANOVA to test for a time x group interaction. Third subjects' ratings of pain and fatigue after each therapy session will be compared the pain and fatigue ratings, to determine if there was unacceptable to subjects.

The level of significance used will be $p < 0.05$.

Analysis for Neuroimaging scans: Biological correlates of the tsDCS and training will be obtained by computing white matter fiber integrity measures of the CST using diffusion tensor imaging an analysis in AFNI (Cox, 1996) and DTI Query (Sherbondy et al, 2005). Integrity measures will include fiber tract density, strength, and their interaction (Ellmore et al 2011), as well as a comparison of parallel and perpendicular diffusivities to investigate changes in axonal integrity and myelination, respectively. We specifically predict that tsDCS combined with repetitive training will result in increased white matter integrity, including increased fractional anisotropy, increased tract density, and changes in axial and radial diffusivities that are consistent with improved myelination and axonal coherence.

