Exoskeleton-training: Patients with acquired brain injury sometimes develop pain or discomfort in the shoulders and arm. In an ongoing study in our laboratory with subjects who are undergoing robotic-exoskeleton exoskeleton training for three- hours per session and three-sessions per week for four weeks, didn't show any significant fatigue, discomfort or pain lasting longer than 24 hours after training ([name] et al, 2012). If there is evidence that pain or

fatigue is worsened by the therapy, the sessions will be reduced or discontinued. All therapy sessions will be supervised by a project staff member. **Assessment/Questionnaires:** All assessments will be performed in a designated room inside Motor Recovery Laboratory. None of these tests are either painful or uncomfortable to perform. In order to prevent potential embarrassment during the testing the test will be done individually and in private. If subjects feel uncomfortable in answering any of the questions they may stop the study at any time.

9. POTENTIAL BENEFITS:

As with any study focusing on basic research, the subjects will derive no direct benefit. The results of these studies may benefit subsequent future subjects if combined spinal stimulation with repetitive training via a exoskeleton device proves to be effective when compared to cortical stimulation with repetitive training. We envision that in the near future the information obtained from the proposed research will provide a better understanding for treatment options of upper extremity motor function in acquired brain injury.

The benefits of participating in this study may be improved arm and hand movement. However, there may be no benefit from participating in this study.

10. RISK-BENEFIT RATIO:

The potential improvement of arm and hand movement outweighs the risk of non-invasive spine stimulation, fatigue, pain and discomfort.

11. CONSENT PROCEDURES:

Informed consent will be obtained from the subject at Motor Recovery Laboratory at The Institute for Rehabilitation and Research. After the patient is identified by the PI and her research team study criteria and he/she is interested in participating, informed, written consent will be obtained by a member of the research team.

In addition a photography/videotaping consent will be obtained from the subject, if he/she agrees to be photographed / videotaped during the assessments or treatment sessions.

12. CONFIDENTIALITY PROCEDURE:

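### The only comparison between conditions is a repeated-measures ANOVA with no time points and no rule for incomplete participants; its classical form drops anyone with one missing cell, which 15 people can ill afford.

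*Combined protocol and SAP*

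**What the plan says.** Section 4 (Description of Study) sets the design: "The study will use cross-over, randomized, sham controlled, double-blinded design", with 15 participants who each receive anodal, cathodal and sham stimulation in random order. The note to Table 1 adds "The subjects will undergo same study schedule in second and third treatment arms", and the paragraph on post-treatment and follow-up assessment says "Month-1 assessment will serve as the baseline assessment of the next treatment arm". Up to 42 visits per person are foreseen.

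Section 7 (Data Analysis) plans a paired t-test of after treatment against baseline within each condition. For the comparison between conditions it offers only "a between groups will examine the effects of treatment by using a repeated measures of ANOVA to test for a time x group interaction". It does not list the time points, say which factors are within or between participants, or mention period or sequence. Its one fallback, transformation or non-parametric methods, is for violated assumptions. Neither it nor any other section gives a missing-data method, an analysis population, a dropout allowance or a replacement rule.

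Two other places bear on missing visits. Section 6 (Subject Enrollment) states "Once enrolled, the subject may pause or terminate his/her participation at any time during the study". Section 8, under exoskeleton training, says that where there is evidence that pain or "fatigue is worsened by the therapy, the sessions will be reduced or discontinued".

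**The concern.** Every participant is meant to pass through every condition, so condition and time both vary within the person. Classical repeated-measures ANOVA needs a full row of cells for each person. Someone who finishes two arms and leaves, or who misses a single assessment that enters the model, is removed from the treatment comparison along with all the data already collected. The within-condition t-tests do not repair this, because they do not compare conditions.

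Two things are at stake. The first is precision: 15 people is a small base, and scattered missed visits cost whole participants. The second is who remains. If pain, fatigue or lack of benefit leads people to miss visits or stop, the comparison rests on those who tolerated all three conditions. In addition, a rule for incomplete people chosen after the data are seen leaves the result open to challenge.

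**Working it through.** **Starting figure.** The plan's sample size of 15 cannot be reproduced, because the documents give no effect size, standard deviation, power or dropout figure. It is taken as given.

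**Visits that must be complete.** From Table 1 and the sharing of the month-1 visit:
- All time points: 1 baseline + 3 arms × 3 later assessments = 10 distinct assessments per person, 15 × 10 = 150 in all.
- Baseline and Visit 13 only: Visit 2, three Visit 13s, and the two month-1 visits that serve as baselines for arms two and three = 6.
- Deletion arm by arm, if the arms were treated as separate groups: 4.

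**Expected complete participants.** The rates are assumptions. Let m be the chance of missing an assessment, w the chance of withdrawing in an arm before its Visit 13, and k the number of visits required. With independent misses, the expected number is 15 × (1 − w)³ × (1 − m)^k. For example, w = 0 and m = 2% with k = 10 gives 15 × 0.98^10 = 12.3; w = 10% and m = 5% gives 15 × 0.729 × 0.599 = 6.5.

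**Variance of an arm contrast at Visit 13.** This was simulated with 15 people, near-balanced sequences, participant, period and treatment effects, and 2,000 runs per setting. The complete-participant variance is compared with that from every arm in which baseline and Visit 13 are both observed. Spans show the spread over repeat runs.

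| w per arm | m per visit | Complete, k = 10 | Extra variance | Complete, k = 6 | Extra variance |
|---|---|---|---|---|---|
| 0% | 2% | 12.3 | 18–19% | 13.3 | 7% |
| 5% | 2% | 10.5 | 23–24% | 11.4 | 11–12% |
| 5% | 5% | 7.7 | 68–69% | 9.5 | 26–27% |
| 10% | 3% | 8.1 | 45–46% | 9.1 | 22–23% |
| 10% | 5% | 6.5 | 74–79% | 8.0 | 33–34% |

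The top figure is the least stable, because runs with very few completers weigh heavily in the average. Part of the k = 10 inflation arises because follow-up visits are required that a Visit 13 contrast does not use. The k = 6 columns remove that part.

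**Deletion arm by arm (k = 4, no withdrawals).** 15 × 0.98^4 = 13.8 per arm at 2% missed and 15 × 0.95^4 = 12.2 at 5%.

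**By count.** If 5 of the 150 assessments are missed at random, 4.4 people are lost on average (about 30% of 15). The loss is smaller if the misses cluster in one or two people.

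**Detectable effect.** For a paired contrast at two-sided 0.05 and 80% power (noncentral t), the smallest detectable difference is 0.78 SD of the paired difference with 15 people, 0.89 with 12 and 1.16 with 8.

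**The case against.** The plan never says that incomplete participants are deleted. Deletion is a property of the classical method. The 10-visit model is also only one reading: the sentence before the ANOVA compares after treatment with baseline, and the primary variable in Section 7 is a change, so a two-level time factor is at least as natural. The reference to groups could even mean that arms are handled separately, which would lose fewer people, although it would ignore that the same people are in each arm. All of this stands, and it is why the size is given as a range.

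A reader might infer that the protocol expects dropout and that the result will be biased towards those who tolerate treatment. The documents do not support that. Section 6 states a right to pause or leave, not a forecast. The wording in Section 8 is conditional, and the same paragraph reports that longer sessions in the laboratory's earlier work caused no significant fatigue, discomfort or pain beyond 24 hours. Table 1 gives windows of ±3 to ±5 days for rescheduling assessments. A person with reduced sessions who still attends the assessments is not missing at all. Nothing indicates that dropout would differ by condition.

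A mixed model also does not cure dropout driven by unrecorded tolerability. That is true, and it calls for an added sensitivity analysis; it is not a reason to keep the ANOVA.

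None of this supplies the missing rule. Whichever time points are meant, the classical within-participant form discards people whose data are usable.

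**Conclusion.** The concern holds as a weakness in the stated method and should be corrected. Section 7 names a method whose usual form cannot use incomplete participants, in a long crossover of 15 people, and nothing elsewhere offsets this. Under the assumed rates, the expected number of complete participants is about 12.3 down to 6.5 with all 10 assessments and about 13.3 down to 8.0 with baseline and Visit 13 only. The variance of an arm contrast at Visit 13 is about 19% to 79% larger in the first case and 7% to 34% larger in the second. Deletion per arm would cost less.

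These sizes rest on missing rates that the documents do not give, on independent misses, and on a choice of time points that the plan leaves open. The larger range is the worst-case reading and should not be quoted alone. Selection of people who tolerate treatment remains a plausible risk only.

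**What to change.** In Section 7, replace the repeated-measures ANOVA with a likelihood-based linear mixed model fitted to all available arm-visits. Include treatment, period, sequence, time and treatment-by-time terms, a participant random effect, and a small-sample degrees-of-freedom correction such as Kenward-Roger. Name the time points that enter and the one that carries the main contrast, and say how the shared month-1 visit is used. Analyse each arm as assigned, whether or not sessions were reduced, and attempt Visit 13 in everyone who starts an arm. Report the complete-participant analysis as a sensitivity check.

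The model has a downside. It relies on data being missing at random given what was observed, and on a covariance structure that 15 people can only partly inform. Prespecify that structure, and add a simple sensitivity analysis for tolerability-related dropout.

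Section 4 gives the last follow-up as month 1 in one sentence and as 3 months in another, while Table 1 shows 1 month. These must be reconciled, because they determine which visits enter.

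The cost is a revision of Section 7 and that reconciliation. It needs no new participants and no visits beyond those scheduled.

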Rationale for exoskeleton-assisted training of arm and wrist movements: There is evidence that treatment intensity has a profound effect on motor recovery and the use of robotic exoskeleton devices has potential to automate labor-intensive therapy procedures (Backhus et al., 2010; Sanchez et al., 2006). In this context, rehabilitative robotic exoskeleton devices can deliver high-dosage, high-intensity repetitive training of single joint movements or functional tasks by coordinated multi joint movements and can provide immediate feedback about performance. Our research team at NeuroRecovery Research Center at TIRR /Memorial Hermann, demonstrated that robotic exoskeleton- assisted training can provide positive gains in arm and hand functions in neural recovery ([name] et al., 2011; Kadivar et al., 2011). These observations have been supported by others (Zarrifa et al., 2011; Cortes et al., 2013).

3. PURPOSE OF THE STUDY:

The purposes of this project are: a) to evaluate if adults with chronic acquired brain injury can improve their upper-limb voluntary movement by participating in a therapeutic program that combines non-invasive spine stimulation with exoskeleton-assisted training (E-A training) to investigate neuroanatomical and neurophysiological mechanisms of therapeutic improvement. Our preliminary data and the literature support the model that augmentation of activity in spared corticospinal tract (CST) axons is a critical mechanism of motor improvement, and furthermore that CST activity can be increased by repetitive motor training and by electrical stimulation of the cervical spinal cord. Therefore, our project will address the goals of providing a direct, beneficial impact to persons with acquired brain injury while, at the same time, investigating the mechanisms that result in improved function.

4. DESCRIPTION OF STUDY:

Fifteen patients with weakness on one side of the body due to stroke ABI will receive ten sessions combined treatment of 20 minutes of 2.5 mA anodal, cathodal, and sham tsDCS over cervical spine combined with high intensity exoskeleton-assisted arm training, five days a week, for 2 consecutive weeks.

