TIRR Outpatient Rehabilitation at Kirby Glen and from the Houston area.

Inclusion Criteria:

1. Providing written informed consent prior to any study related procedures;
2. Age above 18;
3. Diagnosis of acquired brain injury at least for 6 month
4. No neuropsychiatric comorbidities
5. Not being involved in any specific exercise program (e.g., NMES, FES) within the previous 3 months;
6. No planned alteration in upper-extremity therapy or medication for muscle tone during the course of the study;
7. Eligibility for standard upper-extremity rehabilitation at the time of enrollment (i.e., absence medical comorbidities that would prevent standard rehabilitation);
8. No condition (e.g., severe arthritis, extreme shoulder pain) that would interfere with valid administration of the measures or with interpreting motor testing;
9. No contraindications to tsDCS:
 - metal in the head between stimulation area
 - metal in the spine between stimulation area
 - implanted brain medical devices
10. No pregnancy;
11. No contraindications for TMS and MRI based on TMS and MRI screening forms

Exclusion Criteria: Subjects will be excluded if they have:

1. Uncontrolled epilepsy;
2. Any joint contracture or severe spasticity in the affected upper extremity, as measured by a Modified Ashworth Score > than 3 out of 4;
3. History of substance abuse;
4. Subject who cannot provide self-transportation to the study location.

6. SUBJECT ENROLLMENT:

Potential subjects will be identified by the following sources:

1- Flyers will be posted in the TIRR Memorial Hermann outpatient clinic, TIRR Memorial

Herman Adult and Pediatric Outpatient Rehabilitation Kirby Glen, MHH Rehabilitation Centers. Attending physicians and therapists may refer their acquired brain injury outpatients to the study. In order to reach out to individuals with ABI; flyers will be distributed through an e-mail distribution, through social media such as Facebook and LinkedIn and twitter.

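### The cross-over analysis has no period term; adding one is a cheap precision gain whose size depends on a period effect the plan does not quantify

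*Combined protocol and SAP*

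**What the plan says.** Section 4 (Description of Study) sets out a cross-over in which 15 participants receive anodal, cathodal and "sham spinal stimulation experiments for the same duration in a random order". Training is common to every arm, sham included: "In all the experiments participants will receive exoskeleton-assisted training for duration of 1.5 hours", five times a week for two weeks. The Table 1 caption repeats the schedule: "The subjects will undergo same study schedule in second and third treatment arms". The follow-up paragraph of Section 4 links the arms: "Month-1 assessment will serve as the baseline assessment of the next treatment arm".

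Section 7 (Data Analysis) gives two efficacy analyses. The first is: "Within subject comparison of after treatment vs. baseline will be performed, separately for each group, using paired t-test". The second compares the conditions by "using a repeated measures of ANOVA to test for a time x group interaction". Neither analysis, nor any other part of the document, names a term for period or sequence. No scheme for balancing the orders is stated.

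**The concern.** In a cross-over, each treatment contrast is built from arms that sit in different periods. If the gain within an arm depends on whether it comes first, second or third, a model without period either leaves that variation in the error term or, when orders are unevenly drawn, puts part of it into the contrast.

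The document gives three reasons why gains might differ by period.

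- **Recent activity.** Inclusion criterion 5 (Section 5) reads "Not being involved in any specific exercise program (e.g., NMES, FES) within the previous 3 months". The first arm therefore follows 3 months without such a program, while later arms follow ten or twenty training sessions.
- **Training effect.** The rationale for exoskeleton training in Section 2 says that robotic exoskeleton-"assisted training can provide positive gains in arm and hand functions in neural recovery". A first course may not give the same gain as a second or third.
- **Practice.** The Jebsen-Taylor test (JTHFT) and the Fugl-Meyer assessment (FMA) are given repeatedly, so the first change score may contain more practice than later ones.

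Section 4 names the FMA as primary and Section 7 the JTHFT; this point is the same for either. At stake is the precision of the anodal-sham and cathodal-sham comparisons in a trial of 15 people.

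**Working it through.** The plan states no power, effect size or SD, so there is no figure of its own to reproduce. The check uses the schedule, exact arithmetic and a simulation with an assumed period effect.

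**Schedule (Table 1).** Training ends on Day 15 (±3) and the month-1 visit is Day 45 (±5). The gap is 45 − 15 = 30 days, from 40 − 18 = 22 to 50 − 12 = 38. The next first session is on Day 4 (±3) counted from a Day 1 baseline, which adds 3 days (0 to 6): about 33 days, range 22 to 44. FMA and JTHFT are given at baseline, post-treatment, week 1 and month 1. With month 1 reused as the next baseline, the baseline-to-post change spans administrations 1 to 2 in arm 1, 4 to 5 in arm 2 and 7 to 8 in arm 3.

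**Model (assumed).** Change score (post-treatment minus that arm's baseline) = participant + treatment + period + error. The error SD is sigma, n = 15, and group is taken as a within-participant condition. The period pattern is (D, 0, 0), where D is the excess gain in the first arm. There is no carry-over. D/sigma is varied from 0 to 1.5.

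**Chance shift with unrestricted orders.** For anodal minus sham, each participant scores +1, 0 or −1 for which of the two came first, with probability 1/3 each and variance 2/3. The difference in the share going first has SD √((2/3)/15) = 0.211, so the contrast shifts by about 0.21 D (1 SD). The contrast's own SE is sigma·√(2/15) = 0.365 sigma. At D = 1 sigma the shift is 0.211/0.365 = 0.58 SE. A linear pattern (D, D/2, 0) gives √(0.5/15) = 0.183 D instead.

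**Loss of precision without the term.** The SE is inflated by √(1 + D²/(3 sigma²)): 1.04, 1.15 and 1.32 at D = 0.5, 1 and 1.5 sigma.

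**Power for a true anodal-sham difference of 1 sigma (simulated, two-sided 5%), without vs with the period term:**

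| D / sigma | Unrestricted orders | Near-even orders (2 or 3 each) |
|---|---|---|
| 0 | 75 vs 72% | 75 vs 75% |
| 0.5 | 71 vs 72% | 72 vs 75% |
| 1 | 63 vs 72% | 63 vs 75% |
| 1.5 | 52 vs 72% | 51 vs 75% |

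Repeat simulations agree to within about 2 points.

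**False-positive rate without the term.** Over all unrestricted draws it stays at about 5% for every D. With near-even orders it falls to about 2.6% at D = 1 sigma and 1.2% at 1.5 sigma, so the test is conservative. It exceeds 5% only once the draw is known to be uneven. The anodal-first and sham-first counts differ by 5 or more with exact probability 0.155. In those draws the rate is about 7%, 12% and 18% at D = 0.5, 1 and 1.5 sigma (12 to 14% and 17 to 21% for the last two across separate simulations). With the term it is about 5% throughout.

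**Cost of the term if D = 0.** Residual degrees of freedom fall from 45 − 15 − 2 = 28 to 26, and t(26)/t(28) = 1.0035. With unrestricted orders the SE ratio has median 1.028, so the CI ratio is 1.028 × 1.0035, about 1.03; at the 97.5th percentile it is about 1.15. With near-even orders the CI ratio is 1.003 to 1.013.

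**Break-even.** Setting √(1 + D²/(3 sigma²)) equal to the CI ratio c gives D = sigma·√(3(c² − 1)). For c = 1.031 this is √(3 × 0.063) = 0.43 sigma. For c = 1.013 it is √(3 × 0.026) = 0.28 sigma.

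**The case against.** The strongest reply is that the harm rests wholly on D, which the document does not give. Section 2 says training can help; it does not say a second course helps less. Below about 0.45 to 0.5 sigma with unrestricted orders the period term gains nothing, and at D = 0 it costs about 3 points of power. A material loss needs a period effect about as large as the treatment effect assumed here. All of that stands, and it limits the priority of the point.

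The second reply is that each arm has its own baseline and the outcome is change. This removes a stable shift in level from earlier training, which is a real protection, but it does not remove a difference in gain.

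The third is that Section 7 may intend something other than the model simulated here. Neither time nor group is defined. Time most naturally means assessment within an arm, given the adjacent comparison of after-treatment with baseline. The ANOVA could also use all four assessments per arm. If group were analysed as a between-participant factor, the power and interval figures above would not apply.

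Three stronger readings are tempting, and the document does not support them.

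- **That the omission biases the treatment comparison or inflates its error rate.** Order is random, so there is no systematic bias, and the overall rate stays near 5%. The 7 to 18% figures describe only the roughly 15% most uneven draws.
- **That participants enter the first arm untrained.** Criterion 5 bars a specific exercise program, and criterion 6 rules out only a planned change in upper-extremity therapy, so other ongoing therapy is not clearly excluded.
- **That 15 participants cannot be balanced.** Three Latin-square sequences of 5 balance period exactly.

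**Conclusion.** The point holds as a low-cost improvement of minor to moderate priority. The plan analyses a three-period cross-over without a period term, and its own features make unequal gains across periods plausible. The consequence is mainly lost precision: about 9 to 12 points of power at D = 1 sigma and 20 to 24 points at 1.5 sigma, against little or nothing at 0.5 sigma and a small loss from the term at zero. Chance imbalance in an uneven draw is a secondary concern. These sizes rest on an assumed D, a 1-sigma treatment difference, baseline-to-post change scores, condition as a within-participant factor and no carry-over.

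**What to change.** Replace the time-by-group sentence in Section 7 with a within-participant model for each arm's change score (post-treatment minus that arm's baseline), with treatment and period effects. Report the anodal-sham and cathodal-sham contrasts with 95% confidence intervals. The per-condition paired t-tests can stay as description; because every arm includes training, they cannot separate stimulation from training or period gains.

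If orders are still to be allocated, balance them by period: three Latin-square sequences of 5 participants each, or all six orders with 2 or 3 each.

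The cost is one sentence and 2 degrees of freedom, with no added visits, data or participants. If there is no period effect, the interval is about 3% wider at the median with unrestricted orders and about 15% wider or more in the worst 2.5% of draws. With balanced orders it is wider by about 1%.

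Two separate, non-essential notes. Section 4 mentions a 3-month follow-up where the visit heading, Table 1 and the Figure 1 legend all give 1 month; this is a wording correction. A sensitivity model with a term for the preceding treatment is optional and should not be the main analysis.
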